## II. Objectives and/or Endpoints

The objective of this pilot study is to determine if PTNS therapy improves OAB symptoms in MS patients. We hypothesize that PTNS will significantly improve OAB symptoms in MS patients. We aim at using both subjective and objective measures to measure change in symptom severity (e.g. decrease in urinary frequency, urgency and incontinence).

The **primary outcome measure** will be assessed using the PGI-I, a self-reported measure of symptom improvement after treatment completion. This is a validated 1-question tool to which patients score their urinary tract condition now as compared to how it was before starting treatment. The score ranges from 1-7, with 1 being very much better and 7 being very much worse. The **secondary outcome measures** will determine change in urinary symptoms including frequency, urgency, and urinary incontinence, using a 3-day voiding diary, and measure quality of life parameters based on OAB symptoms, using the OAB quality of life short form questionnaire (OABq-SF). All questionnaires are grade A survey tools standardly used for the subjective and objective assessment of OAB symptom and symptom bother. PGI-I questionnaire will be completed at end of 4, 8 and 12 treatments, as well as at follow-up visit (Visit 13), as it is a score of self-reported symptom improvement. Secondary outcome measures will be assessed at baseline (prior to visit 1) and at the end of treatment (visit 13). Unlike idiopathic OAB, OAB symptoms in MS do vary typically in relationship to the disease process, thus closer intervals of assessing change are necessary.

**Primary (or general) objectives:** Assess the impact of PTNS therapy in female MS patients on subject-reported symptom improvement using the Patient Global Impression of Improvement (PGI-I) score.

**Secondary (or specific) objectives:** Determine the subjective and objective change in OAB symptoms in response to PTNS therapy using the OABq-SF and 3-day voiding diary.

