## II. Methodology

This is a pilot, single blind, sham-controlled randomized trial. Female MS patients will be recruited by [name] of the Neurology department and by [name] of the PM&R department, as well as private Urology offices. They will be screened by the research nurse coordinator according to the specific inclusion and exclusion criteria.

We anticipate enrolling 34 patients, in this randomized trial, 17 in each study arm. Eligible participants will be consented and randomized into 1 of 2 groups. Patients will be enrolled in the study and randomized:

- After all screening activities have occurred and it has been determined that the patient meets all inclusion criteria without the presence of exclusionary criteria.

Percutaneous Tibial Nerve Stimulation (PTNS) therapy for female patients suffering from  
Multiple Sclerosis

- After the patient agrees to enroll and comply with the study protocol, regardless of study group assignment.

Patients will be randomized 1:1 to active PTNS treatment or Sham treatment.

The process of randomization will be as follows:

Randomization will be performed using a table of random numbers. Randomization envelopes will be provided by the study's biostatistician. Randomization assignment will be to either active PTNS treatment or Sham treatment. The randomization envelopes will be securely stored in a locked cabinet. The Research Coordinator(s) will ultimately be responsible for maintaining the confidentiality and security of the randomization envelopes. The biostatistician will prepare more envelopes, if necessary. After the participant is randomized, staff will complete the **Subject Enrollment and Randomization Log**. The log may be stored in the locked cabinet with the envelopes. Ultimately the log will be stored in the regulatory binder.

[figure not shown]
All patients who enroll will be seen and treated at the Beaumont Urology clinical research suite.

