**VI. Data Analysis Plan**

The primary outcome measure is the PGI-I score. The PGI-I will determine the patient perception of symptom improvement based on a single question. The PGI-I score given by the patient will range from 1-7, with 1 being very much better and 7 being very much worse. Scores

**Percutaneous Tibial Nerve Stimulation (PTNS) therapy for female patients suffering from  
Multiple Sclerosis**

of 1 and 2 will be considered as clinically meaningful improvement in OAB symptoms. The percent of patients with significant symptom improvement will be compared between the active and sham treatment groups using a one-WAY ANOVA test.

The secondary outcome measures include the 3-day voiding diary and the OABq-SF questionnaire. For both, baseline measures will be taken prior to first treatment and again at the completion of treatment. The change in OAB symptoms (e.g. number of daytime voids and urgency episodes) and the change in OAB symptom bother (e.g. how have your symptoms adjusted planned activities?) between baseline and at the end of treatment will be calculated for each study participants. The average change in symptom (bother) will subsequently be compared between active and sham treatment groups using two-WAY ANOVA.

Finally, patient assigned to receive sham treatment have the option to crossover into active treatment after completion of the sham portion. For patients who complete both sham and crossover studies, data from OABq-SF and 3-day voiding diary will be analyzed using a one-WAY ANOVA in which the average values of three time points (baseline, end of sham treatment, end of crossover) are compared.

As this study is a pilot study, no official power analysis was performed. The sample size was chosen based on the limitations of the budget, which was largely driven by the cost of the PTNS and sham needles. A total of 34 patients will be enrolled in the study, 17 per treatment group. The 17 patients that are randomized into the sham treatment have the option of completing the active treatment (crossover). Data (OABqSF, 3-day voiding diary, PGI-I) will continue to be collected during the crossover study and analyzed as described above.

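### The secondary between-arm test is called a two-way ANOVA but has only one factor; name the test correctly and preferably use ANCOVA on the baseline already collected

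*Combined protocol and SAP*

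**What the plan says.** Section II (Objectives and/or Endpoints) says the secondary measures "will determine change in urinary symptoms including frequency, urgency, and urinary incontinence, using a 3-day voiding diary", with quality of life taken from the OABq-SF. There are two measurement times: "Secondary outcome measures will be assessed at baseline (prior to visit 1) and at the end of treatment (visit 13").

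Section VI (Data Analysis Plan) repeats that "baseline measures will be taken prior to first treatment and again at the completion of treatment". It fixes the response as the change "between baseline and at the end of treatment will be calculated for each study participants". The next sentence gives the test: "The average change in symptom (bother) will subsequently be compared between active and sham treatment groups using two-WAY ANOVA".

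The only grouping named for this test is arm. The Methodology section gives the allocation as "Patients will be randomized 1:1 to active PTNS treatment or Sham treatment" and mentions no stratification factor. The size is set by budget, without a power calculation: "A total of 34 patients will be enrolled in the study, 17 per treatment group". No covariate is planned for any secondary outcome.

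**The concern.** A two-way ANOVA needs two factors. Once each patient is reduced to one change value, time has been used up by the subtraction and only arm remains. The sentence therefore cannot be carried out literally. A reader cannot tell whether the label is a slip or a factor was left out.

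Two things are at stake. First, this sentence governs every planned between-arm comparison of the diary and OABq-SF outcomes, so it should identify one analysis. Second, the sample is small and fixed by budget, so any gain in precision has to come from the analysis. The plan collects a baseline for every secondary measure but does not use it as a covariate.

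**Working it through.** **Inputs from the documents.** Two arms, 1:1, 17 per arm (N = 34); two measurement times; one change per patient; baseline available for each measure. The plan states no power, SD or correlation for this analysis, so there is no figure of its own to reproduce.

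**Assumptions.** Approximate normality; two-sided 5% tests; rho = baseline-to-end correlation within arm; k = follow-up SD divided by baseline SD.

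**Step 1: what the described test is.** On one simulated data set of 17 + 17 patients:

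- squared two-sample t on change: 6.481
- one-way ANOVA F on change: 6.481
- repeated-measures arm-by-time interaction F, with a patient term: 6.481

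These are the same test. The described comparison is therefore sound under either of the sensible names.

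**Step 2: ANCOVA against change score.** Take the baseline variance as 1.

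- Change-score variance is proportional to 1 + k² − 2·rho·k.
- ANCOVA variance is proportional to k²(1 − rho²), times 1 + 1/(N − 4) = 1 + 1/30 for chance baseline imbalance.
- Ratio = k²(1 − rho²) / (1 + k² − 2·rho·k) × 31/30.

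Example, k = 1 and rho = 0.5: 0.75 / 1.00 × 31/30 = 0.775.

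| k | rho 0.3 | rho 0.5 | rho 0.7 | rho 0.9 |
|---|---|---|---|---|
| 1.0 | 0.672 | 0.775 | 0.878 | 0.982 |
| 1.3 | 0.832 | 0.942 | 1.024 | 0.948 |
| 0.8 | 0.519 | 0.590 | 0.649 | 0.628 |

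The ratio is largest where the slope of follow-up on baseline (rho × k) equals 1. There it is 31/30 = 1.033. At k = 1, break-even is at (1 + rho)/2 × 31/30 = 1, so rho = 60/31 − 1 = 0.935. At k = 1.3, ANCOVA is the less precise of the two only for rho between about 0.63 and 0.86.

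Put another way, at k = 1 and rho = 0.5, ANCOVA with 17 per arm is about as precise as a change score with 17/0.775 = 21.9 per arm.

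Simulation (100,000 null trials per setting) agreed with these ratios. Type I error was 4.9 to 5.1% for both methods. For an assumed true difference of 0.8 SD with equal SDs, power for change score and ANCOVA was 48% and 64% at rho 0.3, 62% and 73% at rho 0.5, and 83% and 88% at rho 0.7.

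**Step 3: voiding frequency.** Section V (Eligibility Criteria) requires an average of at least 8 voids per day on the initial diary, which is also the baseline. Selection narrows the baseline SD, which raises k and lowers rho within the trial. Suppose, as an assumption, that selection truncates a normal source population at its median. The baseline variance becomes 1 − 2/π = 0.363, and with r the source-population correlation:

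Ratio = (1 − r²) / [(1 − r)² × 0.363 + (1 − r²)] × 31/30

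- r = 0.3: 0.910 / (0.178 + 0.910) × 31/30 = 0.86
- r = 0.5: 0.750 / (0.091 + 0.750) × 31/30 = 0.92
- r = 0.7: 0.510 / (0.033 + 0.510) × 31/30 = 0.97

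Simulation gave 0.86, 0.92 and 0.97 to 0.98. ANCOVA still gains, but less.

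**The case against.** **The plan is valid as it stands.** The sentence before the test fixes the response as per-patient change, and a two-sample comparison of change between randomized arms is unbiased with correct type I error. This stands. What remains is an unspecified label and an available gain in precision, in the secondary outcomes of a pilot.

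**The author may have meant arm by time.** This cannot be ruled out. If a patient term was intended, step 1 shows that the result is identical to the change-score test. The fair statement is that the second factor and the repeated-measures structure are not specified. Nothing shows that the intended analysis was wrong.

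**The stronger reading.** A reader might infer from the label that the team will fit an unpaired arm-by-time ANOVA to the 68 raw values. The next paragraph of section VI may encourage this, since it plans a "one-WAY ANOVA in which the average values of three time points (baseline, end of sham treatment, end of crossover) are compared" in the same patients and names no within-patient term. That analysis would be invalid. At rho 0.3 to 0.9 with equal SDs, its interaction test has a size of 2.0% falling to 0.0%, and its arm main effect a size of 8.5% rising to 15.6%. But the documents do not describe it: they compute change per patient first, and the crossover paragraph concerns a different analysis. These error rates are a caution about the label and are not a property of the plan.

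**The gain is unknown.** True, since neither rho nor k is given, and for voiding frequency it is probably modest. The possible loss, however, is bounded at about 3%.

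**Counts with many zeros.** Incontinence episodes may fit a linear model poorly. In simulations with 42 to 82% zeros at baseline (assumed), both methods were conservative: size was 2.2 to 4.0% for change and 2.5 to 3.9% for ANCOVA. ANCOVA had 0.60 to 0.69 of the change-score variance. This gives no reason to prefer the change score there, and no support for a rule that switches test at some observed share of zeros.

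**Conclusion.** The concern holds as a matter of specification and precision. The plan names a two-way ANOVA for a comparison with one factor, and does not use the collected baseline as a covariate. It does not hold as a claim of bias or inflated error, because the comparison described is valid.

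Under assumed equal SDs, ANCOVA would cut the variance by roughly 33%, 22%, 12% and 2% at rho 0.3, 0.5, 0.7 and 0.9. For voiding frequency the cut is nearer 14%, 8% and 2 to 3% at source-population correlations 0.3, 0.5 and 0.7 with truncation at the median. At worst the variance rises by about 3%. All of this rests on assumed correlations, SD ratios and near-normality. The primary PGI-I analysis is not affected. The change is worth making because it costs almost nothing.

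**What to change.** Replace the two-way ANOVA sentence in section VI with, for example: *For each OABq-SF scale and diary variable, the Visit 13 value will be compared between arms by ANCOVA with arm as factor and the patient's own baseline value as covariate, reported as an adjusted mean difference with 95% CI.*

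If the change score is kept, call it a two-sample comparison of per-patient change (equivalently, the repeated-measures arm-by-time interaction with a patient term) and delete the two-way label.

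The cost is one sentence and, for ANCOVA, one degree of freedom. It needs no new data, visit or patient: anyone who contributes a change score already has both values that ANCOVA needs.

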**Open-Label:**

At visit 13, after completion of all research related activities, patients will be unblinded to treatment. Patients who were assigned to the sham arm, will be given the option to complete active PTNS therapy and receive open label treatment. If agreed, visit 13 outcome measures will subsequently be used as baseline measures to assess the effect of PTNS therapy on treatment.

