**One week post treatment follow-Up visit: Visit 13: (1 week  $\pm$  3 days from treatment 12)**

One-week post-final weekly treatments ( $\pm$  3 days), participants will return for an office visit. PGI-I, OABq-SF, and 3-day voiding diary will be collected, and a urinalysis completed. We will also assess for adverse events and concomitant medications at this visit. After all study activities are complete, patients will be un-blinded. Those who were in the sham arm will be offered the opportunity to crossover to the open label treatment phase of the study. Subjects in the open label phase will be offered the same scheduled treatments and follow up as those in the initial active PTNS treatment group. They will have up to 7 days to decide and begin treatment if they would like to continue to the open label treatment phase. Open label treatment 1 may also begin the same day as visit 13 if the patient chooses. Medication may be resumed after study completion.

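### The sham-to-open-label comparison uses only patients who chose PTNS after unblinding and completed it, so its Visit 13-to-end change can be biased and should be labelled descriptive

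*Combined protocol and SAP*

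**What the plan says.** Four provisions of the combined protocol and SAP bear on this.

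- **Unblinding** (Methodology, A. Study Intervention, Open-Label): "At visit 13, after completion of all research related activities, patients will be unblinded to treatment".
- **Choice** (same paragraph): "Patients who were assigned to the sham arm, will be given the option to complete active PTNS therapy and receive open label treatment". The Visit 13 section adds: "They will have up to 7 days to decide and begin treatment".
- **Reference value** (Open-Label): "visit 13 outcome measures will subsequently be used as baseline measures to assess the effect of PTNS therapy on treatment".
- **Analysis** (section VI, Data Analysis Plan): "For patients who complete both sham and crossover studies, data from OABq-SF and 3-day voiding diary will be analyzed", by a one-way ANOVA "in which the average values of three time points (baseline, end of sham treatment, end of crossover) are compared".

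Section VI also plans a separate comparison of mean change from baseline to end of treatment between the active and sham groups. That one covers the sham arm as a whole. Nothing in the documents describes the crossover analysis as non-randomised or descriptive, asks for acceptors to be compared with decliners, or says who is expected to accept.

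**The concern.** Sham patients rate their symptoms at Visit 13, learn that they had sham, and then decide whether to take 12 more weekly treatments. The Visit 13 reading can influence that decision, and the same reading is the pre-treatment value for the PTNS effect. If patients with a poor Visit 13 are more likely to accept, part of that poor reading is temporary, and the next reading will tend to be better whatever is given. The objectives section says OAB symptoms in MS vary with the disease process, so some within-patient fluctuation is to be expected.

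Restriction to completers adds a second filter, since patients who do not benefit may stop. The phase is also open label with no concurrent control, so expectation can add to the change. At stake is a within-patient result that could read as little change on sham followed by improvement on PTNS, and be taken as support for the later multi-institutional trial.

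**Working it through.** **Plan's own figure.** There is none to reproduce. Section VI states that no power analysis was done, and 17 + 17 = 34 is consistent. At most 17 sham patients can cross over.

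**Assumptions not in the documents.** Baseline (B), Visit 13 (V) and end of crossover (C) each have SD 1, higher is worse, with a common between-visit correlation ρ of 0.5 or 0.7. Neither sham nor PTNS has any effect. Uptake p is varied.

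**Strict selection.** Suppose the worse fraction p at Visit 13 crosses over, that is, V above a cut z. Then the mean of V among crossers is φ(z)/p, and the mean of both B and C is ρ·φ(z)/p. The spurious improvement from V to C is therefore

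(1 − ρ) × φ(z)/p,

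with an equal spurious worsening from B to V.

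| Uptake p | φ(z)/p | ρ = 0.5 | ρ = 0.7 |
|---|---|---|---|
| 1.00 | 0 | 0 | 0 |
| 0.90 | 0.195 | 0.10 SD | 0.06 SD |
| 0.75 | 0.424 | 0.21 SD | 0.13 SD |
| 0.70 | 0.497 | 0.25 SD | 0.15 SD |
| 0.50 | 0.798 | 0.40 SD | 0.24 SD |

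Simulation gives the same values. If instead the *less* bothered cross over, symmetry reverses the sign and PTNS looks worse by the same amount.

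**Weaker selection.**
- Graded choice (odds of accepting multiplied by 1.5 to 3 per SD of V): 0.04 to 0.15 SD at about 68% uptake, and 0.01 to 0.07 SD at about 88%.
- Choice unrelated to V, or dependent only on stable severity: 0.00 SD.

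**Compared with noise.** With 13 crossers, the SD of the mean V-to-C change is about √(2(1 − ρ)/13): √(1/13) = 0.28 SD at ρ = 0.5 and √(0.6/13) = 0.21 SD at ρ = 0.7. When choice is half-correlated with V, the bias is 0.06 to 0.10 SD, well inside that noise.

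**Effect on the test.** Read as an ordinary unpaired one-way ANOVA, the planned test ignores the pairing and is conservative. With no selection and no entry cut it rejects in under 1% of simulated trials. With 13 of 17 crossing over it rejects in 0.15% to 0.8% (half-correlated choice) or 0.4% to 3% (strict selection on V). It exceeds 5% only in harsher cases: when choice follows the worst change from baseline at ρ = 0.5, rejection is 5.4% at 70% uptake and 16.7% at 50%. A paired V-versus-C test, which the plan does not specify, would favour PTNS falsely in 5–6% (90% uptake), 10–13% (70%) and 13–20% (50%) under strict selection on V, against a nominal 2.5%.

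**Entry criteria.** Section V requires at least 8 voids per day and a score of at least 4 on the first OAB-q item, so baseline is itself selected to be high. With an assumed entry cut at the median, ρ = 0.5 and strict selection at 70% uptake, the whole sham arm improves by 0.40 SD from B to V. The crossers improve by only 0.03 SD, then show a spurious 0.27 SD gain on PTNS. The subset's first step understates the arm's change by 0.40 − 0.03 = 0.37 SD. The entry cut alone lifts the ANOVA's rejection rate to 19% at full uptake with ρ = 0.5; that is a separate regression effect, not crossover selection.

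**The case against.** The strongest reply is that selection on a poor Visit 13 is inferred. Two features of the protocol point away from it. The background section says PTNS is not covered by insurance in MS, so nearly all sham patients may accept, and the bias then largely disappears. Section V keeps antimuscarinics and beta-3 agonists stopped throughout participation, and the Visit 13 section allows them to be resumed only after study completion, so the most bothered patients have a reason to decline. This objection stands: the direction cannot be asserted.

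A reader might also infer that the plan never shows the sham change for the full arm. It does, through the randomised comparison of mean change in section VI. A reader might infer that the crossover subset will necessarily show no change on sham. The entry criteria push towards apparent sham improvement, so that pattern is not assured. Finally, the crossover is not among the stated objectives, and the documents say the study's data as a whole, not this result in particular, would support a later trial.

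The reply does not remove the structural problem. The analysis set is fixed by a post-unblinding choice and by completion, the value that may drive the choice is the reference value, and the plan gives no caution about interpretation. A conservative test leaves the reported means biased if selection occurs.

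**Conclusion.** The concern holds conditionally, as a cheap improvement. The three-point comparison can credit PTNS with regression to the mean, open-label expectation and loss of non-completers. Only the first was quantified, and its range, from zero up to 0.40 SD in favour of PTNS or the reverse sign, rests on assumed correlations, uptake and choice rules.

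The tempting stronger reading is that self-selection *will* make sham look worse and PTNS look better by several tenths of an SD. The documents do not support it: they do not say who will opt in, and the upper figures need strict selection of the worse half or three quarters. Nor does the point touch the trial's efficacy conclusion, since the randomised active-versus-sham comparison, including the primary PGI-I outcome, is complete before the choice is made.

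**What to change.** In section VI (Data Analysis Plan):

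1. State that the crossover comparison is descriptive and non-randomised, and that evidence of PTNS efficacy rests on the randomised comparison only.
2. Analyse the Visit 13-to-end change in everyone who starts open label, using all available data, rather than in completers only.
3. Report the numbers offered, accepting, declining and completing open label, with Visit 13 PGI-I, OABq-SF and diary values for acceptors and decliners. This shows whether selection occurred and in which direction.
4. Present the full-arm sham change, already planned, beside the crossover subset, and do not interpret the subset's baseline-to-Visit 13 change as the sham effect.

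The cost is analysis-plan wording and a few reporting tables. The outcomes are already scheduled for collection, and treatment and visits do not change. The downside is a weaker claim from the crossover phase.
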